### **Prior/Concomitant Therapy**

19 Current/previous administration of inclisiran.

20 Lomitapide within 12 months prior to randomization.

21 Previous administration of PCSK9 inhibition treatment within 12 months prior to randomization (approved or investigational).

22 Fibrate therapy and derivatives are prohibited.

23 Receiving or has received within 14 days of screening, medication that contains a black box warning for significant QT prolongation.

### **Prior/Concurrent Clinical Study Experience**

24 Participation in another clinical study with a study intervention administered in the last 3 months prior to randomization or 5 half-lives from last dose to first administration of study intervention, whichever is the longest.

- 25 Received another new chemical entity (defined as a compound which has not been approved for marketing) within 30 days of last follow-up to first administration of the study intervention of this study or 5 half-lives from last dose to first administration of study intervention, whichever is the longest.
- 26 Use of other investigational products or investigational devices during the course of the study.

### **Other Exclusions**

- 27 Involvement in the planning and/or conduct of the study (applies to both Sponsor staff and/or staff at the study site or their close relatives).
- 28 Judgement by the investigator that the participant should not participate in the study if the participant is unlikely to comply with study procedures, restrictions and requirements.
- 29 As judged by the investigator, any evidence of disease conditions that, in the investigator's opinion, makes it undesirable for the participant to participate in the trial.
- 30 Previous screening in the present study.
  - Individuals who do not meet the criteria for participation in this study (screen failure) may be rescreened. At the investigator's discretion, participants may be rescreened once during the recruitment period.
- 31 Participants who cannot communicate reliably with the investigator.
- 32 Vulnerable participants, eg, kept in detention, protected adults under guardianship, trusteeship, or committed to an institution by governmental or juridical order.
- 33 Plasma donation within 1 month of the screening visit at the clinic or any blood donation/blood loss > 500 mL (> 400 mL in Japan only) during the 3 months prior to screening visit.

### **Optional Genetic Sampling**

- 34 Exclusion from this genetic research may be for any of the exclusion criteria specified for the main study or any of the following:
  - (a) Previous allogeneic bone marrow transplant.
  - (b) Non-leukocyte depleted whole blood transfusion within 120 days of genetic sample collection.

## **5.3 Lifestyle Considerations**

### **5.3.1 Pregnancy**

Participants will be instructed that if they or their partner becomes pregnant during the study this should be reported to the investigator. The investigator should also be notified of pregnancy occurring during the study but confirmed after completion of the study. In the event that a participant's partner is subsequently found to be pregnant after the participant is included in the study, then consent will be sought from the partner (via the participant's request that their partner contact the study site) and, if granted, any pregnancy will be

### **5.3.2      Meals and Dietary Restrictions**

For all study visits (including screening), participants must be fasted for 8 hours prior to blood sampling for LDL-C and other lipid profile. No fluids will be allowed apart from water, which can be given until 1 hour before blood sampling for LDL-C and other lipid profile.

### **5.3.3      Caffeine, Alcohol, and Tobacco**

Participants who use alcohol may participate in the study unless their consumption is deemed excessive by the investigator.

### **5.3.4      Activity**

Participants should not start any new physical training activities or increase the intensity of their usual physical training from 5 days prior to randomization until the end of the study.

### **5.3.5      Other Restrictions**

Participants should refrain from blood donation throughout the study, including the follow-up period.

## **5.4      Screen Failures**

A screen failure occurs when a participant who has consented to participate in the clinical study is not subsequently randomly assigned to study intervention/entered in the study. A minimal set of screen failure information is required to ensure transparent reporting of screen failure participants to meet the Consolidated Standards of Reporting Trials (CONSORT) publishing requirements and to respond to queries from regulatory authorities. Minimal information includes demography, screen failure details, eligibility criteria, and any SAE.

Participants may be rescreened once if the reason for screen failure was transient (including but not limited to study-supplied equipment failure or unforeseen personal events that mandate missed screening visits). Rescreened participants should be assigned the same participant number as for the initial screening. Individuals who do not meet a specific criterion may have this parameter retested if the investigator determines there is a reason to believe that this was caused by a temporary/transient reason.

## **5.5      Criteria for Temporarily Delaying Administration of Study Intervention – Not Applicable**

## 6 STUDY INTERVENTION(S) AND CONCOMITANT THERAPY

Study intervention is defined as any investigational intervention(s), marketed product(s) or placebo intended to be administered to or medical device(s) utilized by a study subject according to the study protocol.

### 6.1 Study Intervention(s) Administered

#### 6.1.1 Investigational Products

Investigational medicinal product will be allocated via an IRT system and study-site staff will dispense proper bottles to the participants. Additional information regarding the administration of IMP is provided in the Pharmacy Manual.

**Table 4** includes a description of the IMPs used in this study, their dose formulation, unit dose strength, dosage level, route of administration, use, sourcing, and packaging and labeling.

**Table 4** Investigational Products Administered

Arm name	AZD0780	Placebo
Intervention name	AZD0780	Placebo
Type	Drug	Placebo
Dose formulation	Round tablet	Round tablet
Unit dose strength(s)	CCI mg	Placebo to match
Dosage level(s)	CCI mg	Placebo to match
Route of administration	Oral	Oral
Regimen	QD	QD
Use	Experimental	Placebo
IMP	IMP	IMP
Sourcing	Provided centrally by the Sponsor	Provided centrally by the Sponsor
Packaging and labeling	Study treatment will be provided in plastic bottles. Labels for study intervention supplied by AstraZeneca will be prepared in accordance with GMP and local regulatory guidelines	Study treatment will be provided in plastic bottles. Labels for study intervention supplied by AstraZeneca will be prepared in accordance with GMP and local regulatory guidelines

GMP = Good Manufacturing Practice; IMP = investigational medicinal product; QD = once daily.

The placebo to match contains cellulose microcrystalline/microcrystalline cellulose and sodium stearyl fumarate. The film-coat contains poly(vinyl alcohol)/polyvinyl alcohol, titanium dioxide, macrogol/polyethylene glycol, talc, iron oxide yellow/ferric oxide, iron oxide red/ferric oxide, and iron oxide black/ferrosoferric oxide.

Details of the batch numbers will be included in the trial master file and final CSR.

## **6.2 Preparation, Handling, Storage, and Accountability**

The IMP will be supplied by AstraZeneca as labeled bottles (QP released by AstraZeneca) with a study specific label. The labels will fulfill Good Manufacturing Practice Annex 13 requirements and medical device directive for labeling.

No special procedures for the safe handling of AZD0780/placebo are required.

The investigator or designee must confirm appropriate conditions (eg, temperature) have been maintained during transit for all study intervention received at the site and throughout the entire study until authorization is provided for on-site destruction or removal of the IMP, reflecting completion of the study. In the event of a temperature excursion detected at any time during the study, sites will follow the reporting procedures for notifying the Sponsor (or designated party); release of IMP for clinical use can only occur once the event has been reviewed and approval is provided by the Sponsor (or designated party).

Only participants randomized in the study may receive study intervention, and only authorized site staff may dispense proper IMP to participants. Prior to dispensing to study participants, all IMP must be stored in a secure, environmentally controlled, and monitored (manual or automated) area in accordance with the labeled storage conditions with access limited to authorized site staff. Participants will be given instructions around storage of IMP and self-administering IMP at home.

The investigator, or delegated, authorized site staff, is responsible for the IMP accountability, reconciliation, and record maintenance (i.e., receipt, reconciliation, and final disposition records). The Sponsor will be permitted upon request to audit the supplies, storage, dispensing procedures and records, provided that the blind of the study is not compromised.

Further guidance and information for the final disposal of unused study interventions are provided in the Pharmacy Manual.

## **6.3 Assignment to Study Intervention**

All participants will be centrally assigned to randomized study intervention using an IRT/RTSM. The participant numbers will be obtained during screening for all participants, after the signature of the ICF, while the randomization codes will be assigned only to the participants proceeding to the treatment phase of the study. Before the study is initiated, the telephone number and call-in directions for the IRT and/or the log in information and directions for the RTSM will be provided to each site in the IRT/RTSM user manual.

In case of rescreening, the rescreened participants should be assigned the same participant number as for the initial screening.

Participants will be randomized to once daily dosing of placebo or different dose levels of AZD0780. Dosing should be supervised and documented by study staff when study intervention is administered in the clinic. Eligible participants will be randomized across 5 different treatment arms (approximately 75 participants in each arm) in a 1:1:1:1:1 ratio for a

12-week treatment period. The planned treatments arms are AZD0780 [redacted] mg, AZD0780 [redacted] mg, AZD0780 [redacted] mg, AZD0780 [redacted] mg, and placebo. A minimum of 5 participants and a maximum of 10 participants in each arm (a minimum of 25 in total and a maximum of 50 in total) will be allocated to sites in Japan. Separate randomization lists will be generated for Japan and for the rest of the world.

Investigational medicinal product will be available as film-coated oral tablets in labeled bottles containing either AZD0780 tablets or placebo tablets (35 tablets in a bottle).

Returned study intervention should not be re-dispensed to participants.

## 6.4 Blinding

### 6.4.1 Methods for Ensuring Blinding

This is a double-blind study in which the investigational site staff and participants remain blinded during the clinical study.

All packaging and labeling of IMP will be done in such a way as to ensure blinding for all participants, Sponsor, and investigational site staff. Investigators, blinded Sponsor, and investigational site staff and participants will remain blinded to each participant's assigned IMP throughout the course of the study.

In the event of a Quality Assurance audit, the auditor(s) will be allowed access to unblinded IMP records at the site(s) to verify that randomization/dispensing has been performed accurately.

A Sponsor site monitor will perform IMP accountability. In the event that the treatment allocation for a participant becomes known to the investigator or other study staff involved in the management of study participants, or needs to be known to treat an individual participant for an AE, the Sponsor must be notified immediately by the investigator and, if possible, before unblinding.

The following personnel will have access to the randomization list during the study, prior to database lock:

- Those carrying out the packaging and labeling of IMP.
- Those generating the randomization list.
- The Sponsor supply chain department.
- The Investigator in case of a medical emergency where the treatment needs to be revealed due to safety reasons, and then only for the at one concerned participant(s).
- Labcorp Bioanalytical Services LLC (responsible for analyzing the samples).
- In the event of an interim analysis, designated sponsor personnel will be unblinded as part of the Unblinded Review Committee as described in [Appendix A5](#).

The information in the randomization list will be kept from other personnel involved in the conduct of the study in a secure location until the end of the study. No other member of the extended study team at the Sponsor, or any CRO handling data, will have access to the randomization scheme during the conduct of the study. Randomization codes will not be broken for the planned analyses of data until all decisions on the evaluability of the data from each individual participant have been made and documented.

The randomization codes are generated by a validated IT-system and are provided by a third party vendor, who provides and manages the RTSM system.

Sponsor safety staff may unblind the intervention assignment for any participant with an SAE. If the SAE requires that an expedited regulatory report be sent to one or more regulatory agencies, a copy of the report, identifying the participant's intervention assignment, may be sent to investigators in accordance with local regulations and/or sponsor policy.

#### **6.4.2 Methods for Unblinding**

The Investigator has sole responsibility for the medical care of the individual study participants throughout the clinical trial duration. It is the Investigator's independent decision to break the randomization code in the event of an emergency that requires a rapid response. This action does not require the Sponsor's representative approval. To maintain the blinding of the assigned study intervention of other participants the emergency unblinding is performed via a specifically programmed transaction within the RTSM system that only reveals the assigned study intervention of the concerned participant(s). The specific process will be described in the RTSM user manual that will be provided to each site.

Access to the transaction is restricted and emergency unblinding can only be performed by appropriate users. The Sponsor applies two options for emergency unblinding: primary line and secondary line.

The primary line for emergency unblinding grants access only for medically qualified site personnel:

- Principal Investigator (PI)
- Sub-Investigator (SI)

Note: Study Coordinators (SC) and any other non-medically qualified site personnel are not allowed to perform emergency unblinding.

In the unlikely event that the Investigator is unable to access the RTSM system for e.g. technical issues or loss of log-in details, there is an IRT Helpdesk service available to assist, which is available 24 hours per day, 7 days per week.

The secondary line for emergency unblinding is a local back-up solution which only allows an appointed user (Local Safety Unblinder) to reveal the study participant's assigned study

intervention when the primary line point of contact is not available. The local back-up solution is available 24 hours per day, 7 days per week.

If a participant's assigned study intervention is unblinded, the sponsor must be notified within 24 hours after breaking the blind. The unblinding action is reported to the Sponsor without revealing the assigned study intervention to the Sponsor staff.

In conjunction with the investigator, the Sponsor can request unblinding of the assigned study intervention for participant(s) with SAEs that are unexpected and are suspected to be causally related to IMP. If the SAE requires that an expedited regulatory report be sent to one or more regulatory agencies, a copy of the report, identifying the participant's intervention assignment, may be sent to investigators in accordance with local regulations and/or sponsor policy.

## **6.5 Study Intervention Compliance**

When participants are dosed at the site, they will receive study intervention directly from the investigator or designee, under medical supervision. The date, and time if applicable, of dose administered in the clinic will be recorded in the source documents and recorded in the eCRF.

When participants self-administer study intervention(s) at home, compliance with study intervention will be assessed at each visit. Compliance will be assessed by direct questioning and counting returned tablets during the site visits and documented in the source documents and eCRF. Deviation(s) from the prescribed dosage regimen should be recorded in the eCRF.

A record of the quantity of AZD0780 dispensed to and administered by each participant must be maintained and reconciled with study intervention and compliance records. Intervention start and stop dates, including dates for intervention delays and/or dose reductions will also be recorded in the eCRF.

## **6.6 Dose Modification**

No dose modifications are allowed during the study.

## **6.7 Continued Access to Study Intervention After the End of the Study**

There is no planned intervention following the end of the study.

## **6.8 Treatment of Overdose**

For this study, any dose of AZD0780 greater than planned will be considered an overdose. The Sponsor does not recommend specific treatment for an overdose.

In the event of an overdose, the treating physician should:

- Evaluate the participant to determine, in consultation with the Study Clinical Lead, if possible, whether study intervention should be interrupted or whether the dose should be reduced.
- Closely monitor the participant for any AE/SAE and laboratory abnormalities as medically appropriate and at least until the next scheduled follow-up. Refer to Section [8.3.12](#) for details of AE/SAE reporting related to overdose.
- Document the quantity of the excess dose as well as the duration of the overdose.

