### **8.3.4 AEs Based on Examinations and Tests**

Deterioration as compared to baseline in protocol-mandated laboratory values and vital signs, should only be reported as AEs if they meet any of the following:

- Fulfil any of the SAE criteria
- Are the reason for discontinuation of the IMP
- Are clinically relevant as judged by the investigator (which may include but is not limited to consideration as to whether intervention or non-planned visits were required or other action was taken with the IMP, eg, dose adjustment or drug interruption).

If deterioration in a laboratory value/vital sign is associated with clinical signs and symptoms, the sign or symptom will be reported as an AE and the associated laboratory result/vital sign

will be considered as additional information. Wherever possible the reporting investigator uses the clinical, rather than the laboratory term (eg, anemia vs low hemoglobin value). In the absence of clinical signs or symptoms, clinically relevant deteriorations in non-mandated parameters should be reported as AE(s).

Deterioration of a laboratory value, which is unequivocally due to disease progression, should not be reported as an AE/SAE.

Any new or aggravated clinically relevant abnormal medical finding at a physical examination as compared with the baseline assessment will be reported as an AE unless unequivocally related to the DUS.

The results from the protocol mandated laboratory tests and vital signs will be summarized in the CSR.

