3.2 Analysis Sets

A minimum of 5 participants and a maximum of 10 participants in each arm (a minimum of 25 in total and a maximum of 50 in total) will be allocated to sites in Japan. Separate randomization lists will be generated for Japan and for the rest of the world to support exploratory investigation of subgroups, if required outside of CSR and to ensure compliance with the Japanese regulations.

Analysis sets are groups of participants who contributed data points to this clinical trial. Analysis sets are defined in [Table 1](#).

If a participant received study intervention from the wrong kit for only a part of the treatment duration and then switched to another, the associated actual treatment group for that participant will be

- the AZD0780 group if the participant has received any dose of AZD0780 and placebo,
- the AZD0780 treatment group the participant had the longest exposure to if a participant has received multiple doses of AZD0780.

Table 1 – Definition of Analysis Sets

Population/analysis set	Description
Enrolled (ENR)	All participants who sign the ICF.
Randomly Assigned to Study Treatment Set (RAND)	All participants who were randomized. Participants will be analyzed according to the treatment to which they were randomized.
Full Analysis Set (FAS)	All randomized participants who received at least one dose of study intervention. Participants will be included in the analysis according to the treatment to which they were randomized.
Safety Analysis Set (SAS)	All randomized participants who received at least one dose of study intervention. Participants will be included in the analysis according to the treatment they actually received.

PK Analysis Set (PKS)	All participants who received at least one dose of AZD0780 and who had evaluable PK data. Participants will be included in the analysis according to the treatment they actually received.
-----------------------	--

ICF = informed consent form; PK = pharmacokinetic(s).

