3.3.1.5 Definition of study treatment

Study treatment is defined as the randomly assigned study treatment. For details regarding the background lipid lowering statin therapy please refer to Section 5.1 and Appendix F of the latest approved CSP and the Statin eligibility memo.

The study treatment is dispensed in 3 bottles as represented in [Table 4](#). The participant is instructed to take 1 tablet/bottle/day. Treatment compliance is defined in Section [4.1.9](#).

Table 4 – Representation of the Drug Dispensing Scheme

	Bottle A	Bottle B	Bottle C
1 mg	AZD0780 1 mg	Placebo	Placebo
3 mg	AZD0780 1 mg	AZD0780 1 mg	AZD0780 1 mg
10 mg	AZD0780 5 mg	AZD0780 5 mg	Placebo
30 mg	AZD0780 20 mg	AZD0780 5 mg	AZD0780 5 mg
Placebo	Placebo	Placebo	Placebo

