4.1.9 Study Drug Compliance

4.1.9.1 Definitions and Derivations

Percent compliance to treatment will be calculated for each participant based on tablet count as: the number of tablets taken (dispensed minus returned), divided by the number of tablets expected to have been taken, multiplied by one hundred. The number of tablets expected to have been taken is defined as 1 tablet/bottle (3 tablets in total) multiplied by ‘date of last dose minus date of first dose plus one’. If the number of tablets dispensed, or the number of tablets returned, is missing for at least one observation for a participant, compliance is not calculated for that participant.

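### Protocol 6.8 offers dose reduction after an overdose, which 6.6 forbids, and neither document describes a way to make a known reduction under the blind

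*Protocol*

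**What the plan says.** Protocol 6.8 treats any dose above the planned one as an overdose. The treating physician is then to determine, in consultation with the Study Clinical Lead if possible, "whether study intervention should be interrupted or whether the dose should be reduced".

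Protocol 6.6 consists of one rule: "No dose modifications are allowed during the study".

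Two other places use language that fits 6.8 better than 6.6. On start and stop dates, Protocol 6.5 says "including dates for intervention delays and/or dose reductions will also be recorded in the eCRF". Protocol 8.3.4, on when a laboratory or vital-sign change counts as an adverse event, mentions whether "other action was taken with the IMP, eg, dose adjustment or drug interruption".

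SAP 3.3.1.5 describes the supply: three bottles, A, B and C, with contents by arm in Table 4. "The participant is instructed to take 1 tablet/bottle/day". On blinding, Protocol 6.4.1 says "Investigators, blinded Sponsor, and investigational site staff and participants will remain blinded" to each participant's assignment.

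**The concern.** The two protocol sections cannot both be followed if 'reduced' means below the planned dose. The clause matters because it is an instruction for a safety situation, and a physician may have to act on it alone, since consultation with the sponsor's lead is only required where possible.

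A site that tried to carry out a reduction would hold three bottles whose contents it cannot know. The obvious improvisation, stopping one bottle, could leave the active dose unchanged while the physician believes it has fallen. Protocol Table 2 lists QT prolongation as a potential risk that modeling predicted at the doses to be studied, although it also reports no ECG finding of concern in Phase I. False reassurance after an overdose is therefore worth preventing.

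**Working it through.** **Inputs.** Tablet strengths by bottle and arm from SAP Table 4. The bottles should add up to the nominal dose of each arm, and they do:

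- 1 mg arm: 1 + 0 + 0 = 1
- 3 mg arm: 1 + 1 + 1 = 3
- 10 mg arm: 5 + 5 + 0 = 10
- 30 mg arm: 20 + 5 + 5 = 30

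**Formula.** Cut from leaving out one bottle = mg in that bottle / nominal daily dose.

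| Bottle left out | 1 mg | 3 mg | 10 mg | 30 mg | Range |
|---|---|---|---|---|---|
| A | 1/1 = 100% | 1/3 = 33.3% | 5/10 = 50% | 20/30 = 66.7% | 33.3% to 100% |
| B | 0/1 = 0% | 1/3 = 33.3% | 5/10 = 50% | 5/30 = 16.7% | 0% to 50% |
| C | 0/1 = 0% | 1/3 = 33.3% | 0/10 = 0% | 5/30 = 16.7% | 0% to 33.3% |

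The placebo arm has no active dose, so the cut is not defined there.

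**Reading the table.**

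- No bottle gives the same cut in every active arm, so a blinded physician cannot obtain a known reduction by dropping one.
- Dropping Bottle C changes nothing in two of the four active arms (1 mg and 10 mg).
- Dropping Bottle A leaves 5 + 5 = 10 mg in the 30 mg arm and no active drug in the 1 mg arm.
- The spread comes from bottle and arm together. The 1 mg arm alone runs from 0% to 100%.
- Dropping two bottles does not help. Keeping only Bottle A cuts 0%, 66.7%, 50% and 33.3% in the 1, 3, 10 and 30 mg arms.

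**Consequence for reporting, if a bottle were left out.** The rule in SAP 3.2 for assigning an actual treatment group begins "If a participant received study intervention from the wrong kit for only a part of the treatment duration". It covers wrong kits only, so a 30 mg participant taking 10 mg would stay in the 30 mg group. Compliance (SAP 4.1.9.1) pools the bottles: 3 × 84 = 252 tablets expected over 84 days. One bottle omitted for 50 days gives (252 − 50)/252 = 80.2%, still in the 80% to 120% category; 51 days gives 201/252 = 79.8%.

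**The case against.** The best defence is that 6.8 follows directly on the definition of an overdose, so 'reduced' naturally means bringing the participant back to the planned dose. On that reading there is no conflict with 6.6 and no bottle is ever dropped. Neither document tells anyone to drop one: SAP 3.3.1.5 fixes one tablet from each bottle per day, and Protocol section 8 allows no waivers. This reading is plausible, but 6.8 does not state it, and it offers reduction as the alternative to interruption.

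Much of the rest of the defence stands and limits the size of the point:

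- Interruption works in every arm. Protocol 7.1 lets the investigator stop treatment for any safety reason, and 6.4.2 allows emergency unblinding without sponsor approval.
- SAP 4.6.1.1 computes the milligrams administered bottle by bottle and 4.6.1.2 lists individual exposure, so an omitted active bottle would show there afterwards, even if the compliance category did not move.
- The wording in 6.5 describes what is recorded, and that in 8.3.4 is an example. Neither grants permission to reduce.

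Two stronger readings are tempting and are not supported. A reader might infer that the blinded supply can never deliver a reduction, or that the blind would have to be broken. A re-allocation of matched bottles through the IRT is conceivable; it is simply not described, and 6.6 would bar it. The Pharmacy Manual, not available here, may say more about administration.

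A reader might also infer that temporary interruptions leave a hole in the primary estimand. SAP Table 3 lists only premature and permanent discontinuation of study treatment, and SAP 4.2.1.1 and 4.2.1.2 remove data only for listed events handled hypothetically. Measurements around a temporary interruption are therefore kept, and adding a row to say so would change no estimate.

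**Conclusion.** The point holds as a minor correction to a safety procedure. The reduction option in 6.8 conflicts with 6.6 as written, and no described route gives a blinded site a known reduction. The 0% to 100% range is exact arithmetic from SAP Table 4, but it measures what would happen if a site improvised by leaving out one bottle; it is not an effect the plan produces. The documents give no number of overdoses, so no frequency can be attached. Nothing here shows an effect on the primary LDL-C comparison or on the blind as the plan stands.

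**What to change.** In Protocol 6.8, replace the interrupt-or-reduce clause with wording such as: *decide whether to interrupt or permanently stop study intervention; otherwise resume the planned dose, one tablet from each bottle daily. No single bottle may be left out.*

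Removing the reference to dose reductions in 6.5 and to dose adjustment in 8.3.4 would make the text consistent with 6.6, but is optional tidying.

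The cost is one clause in the protocol. No SAP change is needed, no analysis changes, and no data are added or excluded.
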